2.4.1.2 Cumulative dose

Cumulative dose of a study treatment is defined as the total dose given during the study treatment exposure and will be summarized for each of the study treatment components, separately for randomized period, cross-over period, and re-treatment period, except that the cumulative dose for Octreotide in the re-treatment period will not be summarized due to very limited cases (Octreotide is optional in the re-treatment period).

The **planned cumulative dose** for a study treatment component refers to the total planned dose as per the protocol up to the last date of that study treatment component administration.

The planned cumulative dose is not summarized/listed. It is used for relative dose intensity calculations.

The **actual cumulative dose** refers to the total actual dose administered, over the duration for which the subject is on the study treatment as documented in the Dose Administration eCRF.

For patients who did not take any drug the cumulative dose is by definition equal to zero.

2.4.1.3 Dose intensity and relative dose intensity

Dose intensity (DI) for participants with non-zero duration of exposure to each study treatment component is defined as follows:

- DI (dosing unit / unit of time) = Cumulative dose (dosing unit) / Duration of exposure (unit of time).

For participants who did not receive any study drug, the DI is equal to zero. Planned dose intensity (PDI) is defined as the assigned dose by unit of time planned to be given to participants as per protocol in the same dose unit and unit of time as that of the Dose Intensity. DI, PDI and Relative dose intensity (RDI) is defined as:

For Lutathera:

- DI (GBq/week) = Cumulative dose (GBq) / duration of exposure (weeks)
- PDI is 7.4 GBq/8 weeks i.e., 0.925 GBq/week
- RDI (%) = DI (GBq/week) / PDI (GBq/week) *100

For Octreotide LAR:

- DI (mg/week) = Cumulative dose (mg) / duration of exposure (week)
- PDI is the following:
 - 30 mg every 8 weeks for those randomized in the investigational arm after Lutathera infusion i.e., 3.75 mg/week
 - 30 mg every 4 weeks for those randomized in the investigational arm after Lutathera treatment is complete (or if Lutathera has been suspended) i.e., 7.5 mg/week
 - 60 mg every 4 weeks for those randomized in the control arm i.e., 15 mg/week

Note if Octreotide is administrated > 32 weeks (i.e., first 4 cycles) in the randomized period, then PDI = (7.5*duration of exposure (week)-120)/duration of exposure (week).

- RDI (%) = DI (mg/week) / PDI (mg/week) *100

For each study drug (Lutathera or Octreotide), RDI will be summarized by treatment period. Since DI for Octreotide have different schedules between 2 arms, DI will be only presented for Lutathera to avoid any mis-interpretation and mis-comparison of Octreotide dose intensity between 2 arms.

Both categorical and continuous summaries (i.e., mean, standard deviation, etc.) of RDI for Lutathera and Octreotide LAR will be presented by treatment period.

Similarly, since administration of Octreotide LAR is optional in the re-treatment period (expected very few cases), DI and RDI for Octreotide LAR will not be calculated for the re-treatment period.

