1.2 Purpose

The pivotal Phase III NETTER-1 study showed that Lutathera with best supportive care (30mg octreotide long-acting) provided a significant increase in PFS to patients with progressive midgut carcinoid tumors (at enrollment) compared to patients treated with high dose (60 mg) octreotide long-acting. The NETTER-1 patient population included 34.5% of patients with G2 NET (65.5% G1), while G3 NETs were excluded. Only patients progressive on SSAs were eligible (2nd line), SSA-naïve patients were excluded.

The aim of the NETTER-2 study is to determine if Lutathera in combination with octreotide longacting prolongs PFS in GEP-NET patients with high proliferation rate tumors (G2 and G3), when given as a 1st line treatment in comparison to treatment with high dose (60 mg) octreotide longacting. SSA-naïve patients are eligible, as well as patients previously treated with SSAs in the absence of progression. Based on extensive experience with Lutathera as well as octreotide LAR in adult GEP-NET patients, and the relevance of the molecular target in adolescent GEP-NET patients, the study will be open to adolescents aged ≥ 15 years and >40 kg body weight (BW); younger patients are not expected to present with the disease meeting the severity criteria for this trial. Due to the rarity of the disease, and specifically GEP-NETs with the severity assessed in this study, no minimum number of adolescent patients is required. The study has been open to adolescents to ensure that access is not unnecessarily denied.

In addition, in the NETTER-2 study, any progressive patient in the high dose octreotide long acting arm has the option, if eligible, to enroll for post-progression cross-over with Lutathera.

Furthermore, patients who experience disease progression in the Lutathera arm after having received and benefitted from 4 doses/cycles in an initial treatment have the option, if eligible according to criteria described in Section 5.2.2, to enroll for re-treatment phase with Lutathera.

The purpose of the NETTER-2 study is to evaluate the efficacy and safety of Lutathera in patients \geq 15 years of age with Grade 2 and 3 advanced GEP-NET (Ki67 index of \geq 10 and \leq 55%), considered being a candidate for treatment with high dose octreotide long-acting.
2 **Objectives and endpoints**

The study primary, secondary, explorative objectives and endpoints are described in Table 2-1.

Table 2-1. Study objectives and endpoints

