6.1.1.2 Control arm

6.1.1.2.1 60 mg octreotide long-acting (Sandostatin[®] LAR Depot)

Sandostatin[®] LAR Depot (octreotide long-acting) is a pharmaceutical that is available in singleuse kits containing a 6-mL vial of 10 mg, 20 mg, or 30 mg strength for intramuscular injection, a

syringe containing 2.5 mL of diluent, two sterile 1¹/₂" 19 gauge needles, and two alcohol wipes. For prolonged storage, Sandostatin[®] LAR Depot should be stored at refrigerated temperatures between 2°C and 8°C (36°F-46°F) and protected from light until the time of use. An instruction booklet for the preparation of drug suspension for injection is also included with each kit.

In the control arm, patients will receive administrations of octreotide long-acting 60 mg (Sandostatin[®] LAR Depot) at 4-week intervals (+/- 3 days) until the completion of the Treatment Phase (see Treatment Phase definition in Section 3), according to the schedule in Table 8-4 (i.e., two injections of Sandostatin[®] LAR 30 mg per treatment), unless the patient progresses or dies.

Patients who were SSA-naïve before enrolment in the study, should receive first planned dose at 30mg and the second (and subsequent) planned dose(s) at 60mg (full dose).

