2.9 Pharmacokinetic analysis

PK assessments:

Patients in the control arm will yield PK data from blood sampling performed at pre-dose with respect to the octreotide long-acting i.m. injection at week 4, 12, 16 and 24 for the determination of plasma trough levels. These trough levels will be presented descriptively.

Descriptive statistics regarding trough levels of octreotide (n, arithmetic mean, CV% mean, standard deviation (SD), median, minimum and maximum) will be presented for Pharmacokinetic analysis set. Since patients in the control arm can start on a lower dose than that specified for the control arm (60 mg), descriptive statistics will be presented for those who start below 60 mg, those that start at 60 mg, and overall.

In addition, the arithmetic/geometric mean (\pm SD) and median concentration-time profiles over time will be displayed graphically on the linear and semi-log view.

All individual trough levels will be listed using the Full analysis set.

The above PK summary will be generated separately, but not be included in the primary CSR.

PK parameters

Not applicable. No PK parameters will be derived.

Handling of PK data below LLOQ or missing

All concentration values below the lower limit of quantitation (LLOQ) are set to zero by the Bioanalyst, and will be displayed in the listings as zero and flagged. LLOQ values will be treated as zero in any calculations of summary statistics. The number of non-zero concentrations will also be reported in the summary statistics.

Missing values for any PK data will not be imputed and will be treated as missing.

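### Octreotide relative dose intensity (RDI) for SSA-naive control patients is measured against 15 mg/week from the first injection, although the protocol plans a 30 mg first dose, so compliant SSA-naive patients score below 100%

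*SAP*

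**What the plan says.** **Protocol.** Both kinds of patient can enter the trial (1.2): "SSA-naïve patients are eligible, as well as patients previously treated with SSAs in the absence of progression". For control patients naive to SSAs, 6.1.1.2.1 states that they "should receive first planned dose at 30mg and the second (and subsequent) planned dose(s) at 60mg (full dose"). Table 8-4 repeats the rule, and 8.8 Imaging speaks of a dose escalation phase in these patients. The 30 mg start is therefore part of the planned schedule and not a toxicity modification.

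**SAP.** Section 2.4.1.3 gives a general definition: "Planned dose intensity (PDI) is defined as the assigned dose by unit of time planned to be given to participants as per protocol". It then lists PDI values for octreotide. The control-arm entry is "60 mg every 4 weeks for those randomized in the control arm i.e., 15 mg/week", with no SSA-naive or first-dose exception. RDI is dose intensity divided by PDI. Section 2.4.1.2 says that planned cumulative dose "refers to the total planned dose as per the protocol" and that it feeds the RDI calculation, but no formula in 2.4.1.3 uses it. Section 2.9 does recognise the low start: "Since patients in the control arm can start on a lower dose than that specified for the control arm (60 mg"), and it splits the pharmacokinetic summaries accordingly. The RDI section has no such split.

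**The concern.** RDI is meant to show dose received relative to dose planned. A patient who receives exactly the planned doses on the planned dates should score 100%. Under the SAP's rule an SSA-naive control patient cannot do so. The exposure clock starts at the first injection, so the 30 mg cycle counts in the numerator but is compared with a 60 mg plan.

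The shortfall is a constant 30 mg, so its percentage size depends on how long the patient stayed on treatment and not on compliance. The ordering can also be reversed: an SSA-naive patient given 60 mg at the first injection, contrary to the plan, would score 100%, while one treated as planned would score less.

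At stake is the accuracy of the control-arm RDI table, in both its continuous and categorical forms. SAP 2.4.1.3 withholds octreotide dose intensity itself, to avoid misleading comparison between arms, so RDI is the octreotide intensity figure that will be shown.

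**Working it through.** **Inputs**
- Control PDI: 15 mg/week (SAP 2.4.1.3).
- Planned doses, SSA-naive control: 30 mg, then 60 mg every 4 weeks (protocol 6.1.1.2.1).
- Control exposure: from the first injection to 27 days after the last, both days counted (SAP 2.4.1.1).
- Assumed control median PFS: 15 months (protocol 12.8.1, SAP 3).

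**The plan's own figures reproduce.** 60/4 = 15 mg/week. For the investigational arm, 30/8 = 3.75 and 30/4 = 7.5 mg/week. The adjustment for exposure beyond 32 weeks is [32 × 3.75 + (D − 32) × 7.5]/D = (7.5D − 120)/D, so it is built wholly from investigational-arm rates.

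**RDI of a fully compliant SSA-naive control patient with n on-schedule injections**
- Exposure: 28(n − 1) + 27 + 1 = 28n days = 4n weeks.
- Cumulative dose: 30 + 60(n − 1) = 60n − 30 mg.
- RDI under the SAP: [(60n − 30)/(4n)]/15 = 1 − 1/(2n).
- PDI matching the protocol: (60n − 30)/(4n) = (15D − 30)/D with D = 4n, which gives RDI = 100% at every n.

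| n | Weeks | Dose received = planned (mg) | RDI under SAP | PDI matching protocol (mg/week) |
|---|---|---|---|---|
| 1 | 4 | 30 | 50.0% | 7.50 |
| 2 | 8 | 90 | 75.0% | 11.25 |
| 4 | 16 | 210 | 87.5% | 13.13 |
| 7 | 28 | 390 | 92.9% | 13.93 |
| 13 | 52 | 750 | 96.2% | 14.42 |
| 16 | 64 | 930 | 96.9% | 14.53 |
| 19 | 76 | 1110 | 97.4% | 14.61 |

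A compliant pretreated control patient has 60n/(4n)/15 = 100% throughout.

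**Which rows matter.** The first scheduled restaging is at week 16, after injections at weeks 0, 4, 8 and 12. A patient found to have progressed at that scan has normally had at least four injections, so RDI is 87.5% or more. With the SAP's month of 30.4375 days, 15 months is 15 × 30.4375/7 = 65.2 weeks, or about 16 four-week cycles, where the gap is about 3 points.

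**Arm level.** If a share s of a fully compliant control arm is SSA-naive and all patients have n injections, mean RDI = 1 − s/(2n). The documents do not give s, so these shares are assumptions:

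| Assumed share | n = 4 | n = 7 | n = 13 |
|---|---|---|---|
| 25% | 96.9% | 98.2% | 99.0% |
| 50% | 93.8% | 96.4% | 98.1% |
| 75% | 90.6% | 94.6% | 97.1% |
| 100% | 87.5% | 92.9% | 96.2% |

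**The over-32-week note.** It names no arm. Applied literally to a compliant SSA-naive control patient at 52 weeks, it gives PDI = (7.5 × 52 − 120)/52 = 5.19 mg/week and RDI = 14.42/5.19, about 278%. The rows above beyond 32 weeks assume that it does not apply to the control arm.

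**The case against.** The strongest reply is that nothing is miscalculated. 60 mg over 4 weeks is 15 mg/week, the trial describes the control regimen throughout as 60 mg every 4 weeks, and SAP 2.9 itself treats 60 mg as the dose specified for the arm. On that view 15 mg/week is a legitimate reference dose. This stands in part: the point is an internal inconsistency, not an arithmetic error. It does not remove the problem, because the SAP defines PDI by what the protocol plans, and the protocol calls 30 mg the first planned dose. The SAP also adjusts PDI for the investigational arm's planned change of schedule, so a constant PDI is not its general convention.

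A second reply is that the general definition, or the planned cumulative dose in 2.4.1.2, already covers the 30 mg start. The explicit control-arm value is the one that would be programmed, so at best the SAP gives two answers.

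A third reply concerns importance, and it stands. RDI is one of several descriptive exposure summaries, alongside duration, cumulative dose, number of doses and dose changes with reasons. A reader might infer that RDI is the measure by which the trial shows that its comparator was adequately given. The documents assign it no such role: there is no RDI threshold, no per-protocol analysis set and no test that uses it.

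**Conclusion.** The inconsistency is real and minor. For SSA-naive control patients the SAP's fixed PDI contradicts its own definition, and a compliant patient is reported with RDI 1/(2n) below 100%: 12.5 points at 4 injections, 7.1 at 7 and about 3 at 16. The figures assume on-schedule injections and that the over-32-week note is confined to the investigational arm.

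Three stronger readings are not supported. First, a reader might infer that the control arm as a whole will look under-dosed. Compliant pretreated patients score 100%, and without the SSA-naive share the arm-level effect cannot be stated. Second, the 50% and 75% values might be taken as typical of early progression. They require a stop after one or two injections, before the first scheduled scan. Third, a reader might infer some effect on the efficacy conclusions. PFS, the key secondary tests and the type I error rate do not depend on RDI.

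**What to change.** In SAP 2.4.1.3:
- For SSA-naive control patients, set PDI = (15D − 30)/D mg/week, with D the duration of octreotide exposure in weeks. On schedule this equals (60n − 30)/(4n).
- Keep 15 mg/week for control patients previously treated with an SSA.
- State that the over-32-week PDI adjustment applies to the investigational arm only.

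The duration-based form is preferable to one that counts injections. Treatment runs to progression, so there is no fixed planned number, and the count becomes ambiguous when an injection is skipped. For example, take an SSA-naive patient with 20 weeks of exposure and one later injection skipped, who has received 30 + 3 × 60 = 210 mg. With five planned injections, RDI is 210/270 = 77.8%. With four given, it is (210/20)/(210/16) = 80.0%. The duration form gives 15 × 20 − 30 = 270 mg planned, hence 77.8%, without ambiguity.

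The patient flag should be prior SSA use, which protocol 8.1.3 already collects, and not the starting dose received, so that a departure from the planned start remains visible. The cost is a few lines of SAP text and one programming flag. This changes the analysis only and implies no change to dosing.

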3.3 Optional Treatment Extension Phase (cross-over)

In the control arm, any RECIST progressive patient (based on central assessment) has the option to enroll for post-progression cross-over, upon signature of a new consent, to receive maximum 4 cycles of Lutathera (7.4 GBq/200 mCi x 4 cycles; cumulative dose: 29.6 GBq / 800mCi) plus 30 mg octreotide long acting every 8 weeks.

If RECIST progression occurs after Week 72 post the primary end point analysis, the decision to enroll the patient in cross-over will be based on local assessment.

The cross-over phase will last until the completion of four Lutathera administrations after which patients will undergo EOT visit (at Week 28), and proceed to the follow up phase.

After cross-over phase is complete, patients will be followed up for 3 years or until EoS, whichever occurs first (and at least 6 months after the last Lutathera dose administered during cross-over).

The time window to start cross-over treatment with Lutathera in this study is 4 years after last patient randomized.

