5.2.1 Eligibility Criteria for Optional Treatment Extension Phase (cross-over)

Any centrally confirmed RECIST progressive patient has the option to enroll for post-progression cross-over and receive maximum 4 cycles of Lutathera (7.4 GBq/200 mCi x 4 cycles; cumulative dose: 29.6 GBq / 800mCi) plus octreotide long-acting (30 mg every 8 weeks), provided that the following criteria are met:

- Patients have provided a signed informed consent form to participate in the study treatment extension phase, obtained prior to the start of any related procedures.
- Expression of somatostatin receptors on all target lesions (based on post-progression new baseline assessment) documented by CT/MRI scans (Note: Cross-over Eligibility CT/MRI scan doesn't need to be repeated if performed within the previous 12 weeks), assessed by any of the following somatostatin receptor imaging (SRI) modalities within 3 months prior to Lutathera treatment: [68Ga]-DOTA-TOC (e.g. Somakit-TOC[®]) PET/CT imaging (or MRI when applicable based on target lesions), [68Ga]-DOTA-TATE PET/CT (or MRI when applicable based on target lesions) imaging (e.g. NETSPOT[®]), Somatostatin Receptor scintigraphy (SRS) with [111In]-pentetreotide (Octreoscan[®] SPECT/CT), SRS with [99mTc]-Tektrotyd, [64Cu]-DOTA-TATE PET/CT imaging (or MRI when applicable based on target lesions).
- All protocol inclusion/exclusion criteria are met (see Sections 5.1 and 5.2).
- The time window to start cross-over is 4 years after last patient randomized.
- Note: Prior each Lutathera administration a 6-week washout period from last octreotide long-acting administration has to be applied.

If RECIST progression occurs after Week 72 post the primary end point analysis, the decision to enroll the patient in cross-over will be based on local assessment.

Images (Cross-over Eligibility SRI and CT or MRI scan) will be also submitted to the central imaging center for a second review: there is no central 'real time' assessment of the Cross-Over Eligibility SRI uptake; however, the images should be submitted to the central imaging center possibly within 1 month. Images submission is not required for screening failure patients.

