Octreotide long- acting 60 mg	Injection and the	ons to e seco	be ac nd (a	lmini: nd su	stered bsequ	l ever ient) j	y 4 we planne	eeks. ed do	Patier se(s) a	nts wl at 60r	no we ng (fu	re SS/ Ill dos	A-naï∖ e).	ve befo	ore en	rolme	nt in	the s	tudy,	should	l receive fir	st planned	dose at 30mg			
Octreotide SC	Octred	otide s	s.c. ir	ijectio	on ca	n be g	given	as n	eede	d														1		
QoL(QLQ- G.I.NET21, QLQ- C30, EQ-5D-5L)	Х	Х			x			х			Х			х			х			Х		x	X			X
Survival information	Х	Х	Х	х	Х	Х	Х	Х	Х	Х	Х	Х	х	Х	Х	х	х	Х	Х	Х	Х	Х	x	x	х	Х

-TREATMENT PHASE:

- TREATMENT: 60 mg octreotide long-acting injections every 4 weeks (±3 days)
- TREATMENT: Lutathera; 4 administrations at 8±1-week intervals

-OPTIONAL EXTENSION TREATMENT PHASE:

- TREATMENT: 30 mg octreotide long-acting injections to be administered the day after each Lutathera infusion Due to the 6 weeks washout prior to each Lutathera injection, octreotide long-acting 30 mg is administered every 8 weeks during Lutathera treatment. IF REOUIRED. RESCUE TREATMENTS: Octreotide s.c. injections (to be stopped 24 h before each Lutathera infusion).
- 1- Before the PFS primary analysis (i.e. 99 evaluable and centrally confirmed disease progressions or death events), patients continue the Treatment Phase until progression. After the PFS primary analysis, the Treatment Phase duration becomes fixed (72 weeks).
- 2- Any progressive patient (based on central imaging assessment) has the option to enroll for post-progression cross-over to Lutathera, upon signature of a new consent, if the eligibility criteria are met. If RECIST progression occurs after Week 72 post the primary end point analysis, the decision to enroll the patient in cross-over will be based on local assessment.

The EoT visit and evaluation of cross-over eligibility can occur on the same day. If these two visits are done on separate days, EoT can be done remotely by phone, and all applicable assessments can be done at the cross-over eligibility visit. If a patient continues to cross-over, 28-day window for EoT visit does not need to apply.

- 3- Via echocardiography, only in patients with history of congestive heart failure (patients with uncontrolled congestive heart failure (NYHA II, III, IV) aren't eligible according to exclusion criteria).

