2.4.1.1 Duration of exposure to study treatment

The duration of exposure to study treatment will be calculated as:

Duration of exposure to study treatment (days) = **(last date of exposure** to any treatment component) – (date of first administration of study treatment component) + 1

The duration of exposure to any single component of study treatment will be calculated as:

Duration of exposure (days) = (last day of exposure to study treatment component) – (date of first administration of study treatment component) + 1

The **last date of exposure** is defined as follows for the study treatment component:

- For Lutathera, the last date of exposure is defined as the last date of administration + 55 days
- For Octreotide LAR, the rules are the following:
 - For patients randomized in the investigational arm, if the last date of administration occurs after an administration of Lutathera, the last date of exposure is defined as the last date of administration for Octreotide + 55 days
 - For patients randomized in the investigational arm, if the last date of administration occurs after the 6-week washout period of the last dose of Lutathera (i.e., Octreotide starts the every 4 weeks schedule after discontinuation of Lutathera), then the last date of exposure is defined as the last date of administration + 27 days
 - For patients randomized in the control arm, the last date of exposure is defined as the last date of administration + 27 days

This duration of exposure includes the periods of temporary interruption (of any component of the study treatment for any reason). The duration of study treatment exposure and exposure to each treatment component will be summarized by treatment group and by treatment period. In addition, number of cycles and average duration of cycle (for Lutathera only) will also be summarized for single component of study treatment by treatment period.

For analyses related to the cross-over/re-treatment period, duration of exposure to Lutathera will be calculated as above during either the cross-over or re-treatment period as appropriate. Since administration of Octreotide LAR is optional in the re-treatment period (expected very few cases), the duration of exposure to Octreotide LAR will not be calculated for the re-treatment period.

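### Octreotide relative dose intensity in the cross-over period uses the control arm's 60 mg schedule, so a fully adherent cross-over patient is reported at about 29%

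*SAP*

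**What the plan says.** SAP 2.4.1.1 to 2.4.1.3 plan octreotide exposure, cumulative dose and RDI by treatment period. On RDI the SAP states: "For each study drug (Lutathera or Octreotide), RDI will be summarized by treatment period". Section 2.4.1.2 names the cross-over period as one of the periods for cumulative dose. All three sections exempt octreotide in the re-treatment period. None exempts it in cross-over.

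The working rules are set by randomized arm:

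- Planned intensity, control: "60 mg every 4 weeks for those randomized in the control arm i.e., 15 mg/week".
- Planned intensity, 8-weekly octreotide: "30 mg every 8 weeks for those randomized in the investigational arm after Lutathera infusion i.e., 3.75 mg/week".
- End of exposure, control: "For patients randomized in the control arm, the last date of exposure is defined as the last date of administration + 27 days".
- End of exposure in the investigational arm when the last octreotide injection follows a Lutathera dose: "the last date of exposure is defined as the last date of administration for Octreotide + 55 days".

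For cross-over, protocol 3.3 plans up to four Lutathera cycles "plus 30 mg octreotide long acting every 8 weeks". Protocol 5.2.1 gives the same schedule: "plus octreotide long-acting (30 mg every 8 weeks), provided that the following criteria are met". So does the legend of protocol Table 8-4: "octreotide long-acting 30 mg is administered every 8 weeks during Lutathera treatment".

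**The concern.** Every patient in the cross-over set was randomized to control. Read literally, the SAP therefore gives these patients the planned dose and dosing interval of the randomized period they have already left. The 3.75 mg/week and + 55 day entries match the cross-over schedule, but they are restricted to the investigational arm. The SAP's adjustment for octreotide given beyond 32 weeks is restricted to the randomized period, so it does not help either.

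The resulting table would show protocol-adherent cross-over patients as having received less than a third of their planned background octreotide. Their octreotide exposure would also end 28 days earlier than under the SAP's 8-weekly rule. Anyone reading the cross-over safety data would get a false picture of what was given alongside Lutathera.

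**Working it through.** **Inputs**

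- Cross-over octreotide: 30 mg every 8 weeks with up to four Lutathera cycles (protocol 3.3, 5.2.1, Table 8-4 legend). Full adherence is four injections at weeks 0, 8, 16 and 24, or 120 mg.
- First administration is counted within each period (SAP 2.1.1.2), so the cross-over clock starts at the first cross-over injection.
- Duration in days = last injection + tail − first injection + 1, with a tail of 27 or 55 days (SAP 2.4.1.1).
- DI = cumulative dose / duration in weeks; RDI = DI / planned intensity (PDI) × 100 (SAP 2.4.1.3).

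**The SAP's own figures reproduce**

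- 30/8 = 3.75, 30/4 = 7.5 and 60/4 = 15 mg/week, as stated.
- Randomized control, for example six 60 mg injections every 4 weeks: 5 × 28 + 27 + 1 = 168 days = 24 weeks; 360/24 = 15 mg/week; RDI 100%.
- Investigational arm, four 30 mg injections every 8 weeks: 3 × 56 + 55 + 1 = 224 days = 32 weeks; 120/32 = 3.75 mg/week; RDI 100%.

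In the randomized period the rules therefore return 100% for an adherent patient in either arm.

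**Cross-over, four injections at 8-week spacing**

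| Tail | PDI (mg/week) | Duration | DI (mg/week) | RDI |
|---|---|---|---|---|
| + 27 days | 15 (SAP as written) | 168 + 27 + 1 = 196 days = 28 weeks | 120/28 = 4.29 | 28.6% |
| + 27 days | 3.75 | 28 weeks | 4.29 | 114.3% |
| + 55 days | 15 | 168 + 55 + 1 = 224 days = 32 weeks | 120/32 = 3.75 | 25.0% |
| + 55 days | 3.75 | 32 weeks | 3.75 | 100% |

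Only the last row returns 100% for full adherence. The tail and the planned intensity have to change together.

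**Sensitivity of the as-written result**

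- Lutathera may be given at 8 ± 1 weeks. With four injections at 7-week spacing: 3 × 49 + 28 = 175 days = 25 weeks; 120/25 = 4.80; RDI 32.0%. At 9-week spacing: 3 × 63 + 28 = 217 days = 31 weeks; 120/31 = 3.87; RDI 25.8%.
- With fewer injections at 8-week spacing: one gives 30/4 = 7.5 and 50%; two give 60/12 = 5.0 and 33.3%; three give 90/20 = 4.5 and 30.0%.

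No on-schedule patient comes near 100%.

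**The case against.** The strongest objection is that the SAP never says outright that 15 mg/week applies in cross-over. SAP 2.4.1.3 opens by defining planned intensity as what the protocol plans to give, which in cross-over is 3.75 mg/week. A programmer could follow that definition. This is a fair reading, but it does not rescue the plan. The general definition then conflicts with the specific control-arm entry, and combined with the stated 27-day tail it gives 114%. Two programmers could report 29% and 114% for the same patient.

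A second objection defends the 27-day tail. Protocol 3.3 places the cross-over end-of-treatment visit at Week 28, and 196 days is exactly 28 weeks. The + 55 days is also a SAP convention, not a protocol rule. Both facts are correct. However, the SAP already applies + 55 days to Lutathera, including in cross-over, and to investigational-arm octreotide on the same 8-weekly schedule. Keeping + 27 days would end octreotide exposure at 28 weeks and Lutathera exposure at 32 weeks in a patient whose last doses were about a day apart.

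What stands is the limit on impact. Number of doses and cumulative dose are also summarized, so the milligrams given would be visible beside the RDI. Octreotide DI itself is not presented. SAP 2.1.1.10 limits cross-over reporting at the primary analysis to selected key safety output. The SAP's individual divisions are all correct; the fault is which rule is applied to which period.

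**Conclusion.** The point holds. Applied as written, the SAP reports an octreotide RDI of 28.6% for a cross-over patient who received all four planned injections on time, where its own 8-weekly rules give 100%. The range is 25.8% to 32.0% across the ± 1 week window. The result assumes that the listed control-arm entries govern cross-over, since no other listed entry fits these patients. The alternative reading, with the general definition of planned intensity, gives 114% and is also wrong. The consequence is confined to descriptive octreotide exposure tables for the cross-over period. The PFS analysis, the key secondary tests, the type I error, the power and the 99-event target are unaffected. This is a minor correction.

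**What to change.** In SAP 2.4.1.1 and 2.4.1.3, define the octreotide rules by treatment period as well as by randomized arm:

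- Randomized period, control arm: keep 15 mg/week and last injection + 27 days.
- Cross-over period: take the planned intensity from the protocol's existing cross-over schedule (30 mg every 8 weeks, 3.75 mg/week) and set the end of exposure to last injection + 55 days, as the SAP already does for octreotide given after Lutathera in the investigational arm.

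A simpler alternative is to extend the re-treatment exemption for octreotide exposure and RDI to cross-over. That removes the wrong figure but also drops the information.

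Either choice changes only the reporting formula and leaves the dosing schedule alone. The cost of the main fix is two lines of SAP wording and a programming change before the cross-over tables are produced. No new data are needed.
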